3.2 PRIMARY ENDPOINT(S) ANALYSIS

The co-primary endpoints are:

- Percent change in CSF GM2 from baseline to Week 104 in the primary population.
- Annualized rate of change in 9-HPT from baseline to Week 104 in the primary population.

A statistically significant effect should be demonstrated on both primary endpoints to declare superiority of venglustat.

3.2.1 Percent change in CSF GM2

3.2.1.1 *Definition*

The first co-primary endpoint in the primary population is the percent change in CSF GM2 from baseline to Week 104.

3.2.1.2 *Main analytical approach*

This endpoint will be analyzed using an analysis of covariance (ANCOVA) including the fixed effect of treatment (venglustat versus placebo) and the continuous fixed covariate of baseline value.

This model will provide baseline adjusted least-squares (LS) means estimates at Week 104 for both treatment groups with their corresponding standard errors (SEs).

The difference in LS means will be used to compare the venglustat group to the placebo group. The difference in LS means will be presented with its associated SE, 90% confidence interval and one-sided p-value. Statistical significance will be assessed at the one-sided 0.05 level (see [Section 3.1](#) for justification).

In case the results from the ANCOVA may be severely impacted by the presence of outliers (participants with extremely low or high percent change in CSF GM2) the ANCOVA will be replaced by a robust ANCOVA, using Huber's M estimation. The exact criterion to determine whether the robust ANCOVA should be used is presented in [Section 5.6.1.1](#). The robust ANCOVA will also include the fixed effect of treatment (venglustat versus placebo) and the continuous fixed covariate of baseline value.

In case the robust ANCOVA is not used as main analysis, this robust analysis will be produced as sensitivity analysis. If the robust ANCOVA becomes the main analysis, the ANCOVA will be produced as sensitivity analysis.

The number and percentage of participants with values <LLOQ or >ULOQ will also be presented.

In addition, descriptive statistics will be presented on CSF GM2 biomarker by time points. These statistics will include mean, standard deviation (SD), [Q1, Q3], median, minimum, and maximum.

3.2.1.3 *Sensitivity analyses*

3.2.1.3.1 *Analysis with treatment as randomized*

The main analysis described in [Section 3.2.1.2](#) will be conducted according to intervention treatment actually received by participants. In case the treatment actually received is different from the treatment assigned by randomization for at least one participant, the analysis will also be conducted according to the treatment assigned by randomization.

3.2.2 9-hole peg test endpoint for primary population

3.2.2.1 *Definition*

The second co-primary endpoint in the primary population is the annualized rate of change in 9-HPT from baseline to Week 104.

3.2.2.2 *Main analytical approach*

[figure not shown]
The primary analysis will include all data collected in patients from the primary population, regardless of whether or not participants completed the treatment period. Patients who prematurely and permanently discontinue study medication will be requested to continue to be assessed after treatment discontinuation, up to the Week 104 visit. Data collected after treatment discontinuation will be included in the primary analysis. All efforts will be made to minimize the amount of missing data.

The 9-HPT will be derived from the two trials for each hand (see [Section 5.5.1](#) for derivation of the 9-HPT).

Annualized rate of change in 9-HPT will be compared between venglustat and placebo using a linear mixed-effect model.

The model will assume linear change over time in 9-HPT after log transformation. The logarithm transformation was selected due to anticipated non-normal distribution of the 9-HPT. Analysis of natural history data showed that logarithm transformation improved the normality of the distribution and reduced the impact of outliers (see [Figure 1](#)). A logarithm transformation will allow interpretation in terms of relative increase in time to complete the 9-HPT (annual % increase per year).

Figure 1 - Distribution and QQ-plot of Studentized residuals from the linear mixed-effect model on natural history data - With or without log transformation

The model will include separate slopes for the venglustat and placebo arm. In addition, the model will include random intercept and slope in order to account for the between subjects variability. A residual variance will account for the within-subject variability.

The linear mixed-effect model is based on the following equation:

$$y_{ijk} = \alpha_j + \beta_j t_{ijk} + u_{1ij} + u_{2ij} t_{ijk} + \varepsilon_{ijk}$$

Where:

- y_{ijk} is the log-transformed 9-HPT of subject i from group j at the k^{th} assessment.
- t_{ijk} is the time (in years) from randomization of the k^{th} assessment of 9-HPT.
- α_j is the fixed intercept of group j .
- β_j is the fixed slope of group j .
- u_{1ij} and u_{2ij} are the random intercept and random slope of subject i from group j .
- ε_{ijk} is the residual error.

The linear mixed-effect model makes the following assumptions:

$$\begin{pmatrix} u_{1ij} \\ u_{2ij} \end{pmatrix} \sim N\left(\begin{pmatrix} 0 \\ 0 \end{pmatrix}, \begin{pmatrix} \sigma_I^2 & \rho\sigma_I\sigma_S \\ \rho\sigma_I\sigma_S & \sigma_S^2 \end{pmatrix}\right)$$

$$\varepsilon_{ijk} \sim N(0, \sigma_R^2)$$

$$\begin{pmatrix} u_{1ij} \\ u_{2ij} \end{pmatrix} \text{ and } \varepsilon_{ijk} \text{ are independent}$$

Where:

- σ_I^2 is the variance of random intercepts.
- σ_S^2 is the variance of random slopes.
- σ_R^2 is the variance of residual errors.
- ρ is the correlation between random intercepts and random slopes.

For the primary analysis, the linear mixed-effect model will be estimated in a Frequentist framework.

This model will provide mean estimate of the slope of log-transformed 9-HPT with their corresponding SE. A back-transformation (ie, exponential transformation) will be applied to obtain annualized rate of change of 9-HPT (in % per year) within each treatment arm:

$$\text{Annualized rate of change (\%/year)} = [\exp(\text{mean slope of log-transformed 9-HPT}) - 1] \times 100$$

The difference in annualized rate of change will be used to compare the venglustat group to the placebo group. The difference in LS means will be presented with its associated 90% confidence interval (see [Section 5.6.2](#)) and one-sided p-value. Statistical significance will be assessed at the one-sided 0.05 level (see [Section 3.1](#) for justification).

In case the results from the linear mixed-effect model may be severely impacted by the presence of outliers (participants with extremely low or extremely high slope of log-transformed 9-HPT), the linear mixed-effect model will be replaced by the robust ANCOVA on individual slopes, described in [Section 3.2.2.3.1](#). The exact criterion to determine whether the robust ANCOVA should be used is presented in [Section 5.6.1.2](#).

Simulations showed that the linear mixed-effect model is the most powerful approach when the distribution of individual slopes is normal but would be dramatically impacted in case a small proportion of participants exhibit an extreme slope. The Type I error rate of the linear mixed-effect model would also be inflated in presence of extreme slopes. The robust ANCOVA on individual slopes would be slightly less powerful if the distribution of individual slopes is normal, but very modestly impacted in presence of extreme slopes. The proposed approach with a pre-specified criterion for using the robust ANCOVA maintains the power close to 80% in all scenarios and protects against inflation of the Type I error rate. Details on the simulation is provided in [Section 5.6.3](#).

If the robust ANCOVA becomes the main analysis, the linear mixed-effect model will be produced as sensitivity analysis.

3.2.2.3 *Sensitivity analyses*

3.2.2.3.2 *Sensitivity to the logarithm transformation*

A sensitivity analysis will assess the impact of the logarithm transformation.

In this sensitivity analysis, the linear mixed-effect model will be fitted to the 9-HPT without logarithm transformation.

In case of presence of outlier, the linear mixed-effect model will be replaced by the robust ANCOVA on individual slopes, described in [Section 3.2.2.3.1](#). The exact criterion to detect outliers is presented in [Section 5.6.1.2](#).

Another sensitivity analysis will use the reciprocal of the 9-HPT.

3.2.2.3.3 *Sensitivity to the assumption of linear change*

A sensitivity analysis will assess the impact of the assumption of linearity of change. A mixed effect model with repeated measures (MMRM) with the categorical fixed factor of time (representing scheduled visits) will be used. Change from baseline in log-transformed 9-HPT at the different time-points will be included in this model, with the fixed effects of treatment group (venglustat versus placebo), time point (Week 12, Week 26, Week 52, Week 78 and Week 104) treatment-by-time point interaction as well as the continuous fixed covariate of log-transformed baseline 9-HPT.

This model will be run using SAS Mixed procedure with an unstructured correlation matrix to model the within-participant errors. Parameters will be estimated using restricted maximum likelihood method. Denominator degrees of freedom will be estimated using Kenward-Roger approximation. This model will provide baseline adjusted LS mean change at Week 104 for each study intervention groups with their corresponding SE.

A back-transformation (ie, exponential transformation) will be applied to obtain baseline adjusted LS mean percent change at Week 104 within each treatment arm. The difference in LS mean percent change will be presented with its associated 90% confidence interval (similar to [Section 5.6.2](#)) and one-sided p-value.

In addition, the same analysis will be repeated without log-transformation of 9-HPT.

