 - Adult onset GM2 gangliosidosis participants will receive a venglustat 15 mg tablet or placebo once daily in the primary analysis period and will receive a venglustat 15 mg tablet once daily in the OLE treatment period.
 - Adult participants in the secondary population will receive a venglustat 15 mg tablet once daily in the primary analysis period and OLE treatment period.
 - Adolescents and juvenile participants in the secondary population (≥ 2 years of age) will receive venglustat [REDACTED]
As adolescent and juvenile participants grow, venglustat doses [REDACTED]
[REDACTED]
[REDACTED]

Statistical considerations:

- **Sample size calculations:** In the primary population, approximately 57 participants will be randomly assigned with a 2:1 randomization ratio to venglustat (n=38) or placebo (n=19). This sample size will provide approximately 80% power to detect a difference between venglustat and placebo with regards to the primary efficacy endpoint of annualized rate of change in 9-HPT. It will also provide >99% power to detect a difference between venglustat and placebo with regards to the co-primary endpoint of percent change in CSF GM2 biomarker from baseline to Week 104. The sample size for the secondary population up to 20 is not based on statistical power calculation, but on empirical considerations. The Sponsor will attempt to enroll at least 1 participant, aged 2 years or older (or ages 2 to <18 years for juvenile/adolescent late-onset GM2 gangliosidosis), in each disorder. This is in addition to the 57 participants from the primary population.

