3.3.1.2 Main analytical approach

3.3.1.2.1 Absolute change in CSF GM2

The endpoint of absolute change in CSF GM2 biomarker will be analyzed with the same approach used for percent change and described in [Section 3.2.1.2](#).

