4 SAMPLE SIZE DETERMINATION

In the primary population, approximately 57 participants will be randomly assigned with a 2:1 randomization ratio to venglustat (n=38) or placebo (n=19). This sample size will provide approximately 80% power to detect a difference between venglustat and placebo with regards to the primary efficacy endpoint of annualized rate of change in 9-HPT.

Sample size and power calculations were based on simulations (see [Section 5.6.3](#) for details).

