5.6.1.1 Criterion for CSF GM2

Potential outliers will be identified from the standardized residuals, estimated from a robust ANCOVA of percent change in CSF GM2 from baseline to Week 104, with treatment effect (venglustat versus placebo) as factor and the continuous fixed covariate of baseline value.

The robust ANCOVA will be used as primary analysis for the percent change in CSF GM2

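### The CSF GM2 ANCOVA pools one residual variance over a 38:19 split, so the reported SE and 90% CI may be too narrow if venglustat shrinks the spread of percent change

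*SAP*

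**What the plan says.** SAP 3.2.1.2 specifies an ordinary ANCOVA of percent change in CSF GM2: "This endpoint will be analyzed using an analysis of covariance (ANCOVA) including the fixed effect of treatment (venglustat versus placebo", with the baseline value as covariate. On reporting it says "The difference in LS means will be presented with its associated SE, 90% confidence interval and one-sided p-value", and on testing "Statistical significance will be assessed at the one-sided 0.05 level". SAP section 4 sets the size: "approximately 57 participants will be randomly assigned with a 2:1 randomization ratio to venglustat (n=38) or placebo (n=19".

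For this endpoint the readable text contains no arm-specific variance, no heteroscedasticity-consistent SE and no log scale. The additional analyses are the exchange between plain and Huber ANCOVA (3.2.1.2) and a rerun by randomized treatment if any participant received the other one (3.2.1.3.1). Neither addresses unequal variance.

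For absolute change, a secondary endpoint under the Hochberg procedure, SAP 3.3.1.2.1 says "The endpoint of absolute change in CSF GM2 biomarker will be analyzed with the same approach used for percent change". On outliers, SAP 5.6.1.1 says "Potential outliers will be identified from the standardized residuals, estimated from a robust ANCOVA of percent change in CSF GM2", that is, from one fit to both arms. The readable text stops before the cut-off.

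**The concern.** Percent change is 100 × (Week 104 / baseline − 1). If the drug multiplies GM2 by a factor r and the relative variation stays the same, the SD of percent change is also multiplied by r. The same holds for absolute change at a given baseline. The less variable group would then be the 38-participant arm, which dominates the pooled variance, while the 19 placebo participants contribute most of the true uncertainty in the difference. The pooled SE is then too small.

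At stake is the precision reported for a co-primary and a secondary endpoint. The protocol (3.1) expects a GM2 reduction to predict clinical efficacy, so readers will use the size of the effect and its interval as well as the p-value.

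**Working it through.** **Inputs from the documents.** n = 38 and 19; one-sided 0.05; 90% CI; ANCOVA with treatment and baseline, hence 57 − 3 = 54 residual df. Not readable: the GM2 effect size, any SD of percent change, and the GM2 outlier cut-off. The ratio R = SD(venglustat)/SD(placebo) is therefore an assumption, taken over 0.3 to 1.5.

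**The plan's own figure.** The protocol synopsis claims ">99% power to detect a difference between venglustat and placebo with regards to the co-primary endpoint of percent change in CSF GM2 biomarker". Without the effect and SD this cannot be reproduced, but the effect it implies can be found. By the normal approximation, 99% power needs a difference of (1.645 + 2.326) × √(1/38 + 1/19) = 3.971 × 0.281 = 1.12 common SDs.

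**Pooled versus true SE** (placebo SD = 1, baseline adjustment ignored):

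- Pooled: SE² = [(37R² + 18)/55] × (1/38 + 1/19)
- True: SE² = R²/38 + 1/19
- For R = 0.5, pooled: (27.25/55) × 0.07895 = 0.0391, SE 0.198
- For R = 0.5, true: 0.00658 + 0.05263 = 0.0592, SE 0.243
- SE ratio: 0.198/0.243 = 0.81
- Coverage of the nominal 90% CI ≈ 2Φ(1.674 × SE ratio) − 1. This returns 0.906 at R = 1, so it is slightly generous.

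| R | SE ratio | Coverage, formula | Coverage, simulated | Simulated, arm-specific variance |
|---|---|---|---|---|
| 1.5 | 1.14 | 0.944 | – | – |
| 1.25 | 1.08 | 0.929 | – | – |
| 1.0 | 1.00 | 0.906 | 0.899 | 0.898 |
| 0.7 | 0.89 | 0.863 | 0.854 | 0.898 |
| 0.5 | 0.81 | 0.826 | 0.814 | 0.896 |
| 0.3 | 0.75 | 0.788 | 0.776 | 0.898 |

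Simulated columns: normal data, 4,000 trials per row, Satterthwaite df for the arm-specific version. With 34 and 17 participants (10% loss) the pooled values are nearly the same, for example 0.819 at R = 0.5.

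**Log-normal ratio, uniform response** (SD of log ratio 0.15 or 0.3; 38:19). Reductions of 30%, 50% and 70% correspond to R = 0.7, 0.5 and 0.3.

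- Pooled coverage: 0.841 and 0.862 at 30%; 0.817 and 0.806 at 50%; 0.779 and 0.774 at 70%.
- Arm-specific coverage in the same runs: 0.885 to 0.903.

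**Non-uniform response at a 50% reduction** (8,000 trials per cell; baseline log SD 0.5; off-drug participants assumed back at baseline). Pooled coverage:

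| SD of log ratio | Uniform | 5% / 10% / 15% of the arm off drug | Between-patient response SD (log scale) 0.2 / 0.3 / 0.4 |
|---|---|---|---|
| 0.2 | 0.825 | 0.856 / 0.888 / 0.902 | 0.861 / 0.896 / 0.927 |
| 0.3 | 0.812 | 0.849 / 0.867 / 0.869 | 0.839 / 0.866 / 0.887 |

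**Estimate, level and power.** Bias of the least-squares difference was at most 0.2 percentage points. With no drug effect the log-normal model gives equal spreads; simulated one-sided rejection was 0.057 and 0.050 (log SD 0.15 and 0.3) for the pooled test. Power with arm-specific variances was 0.988 or more wherever an effect was simulated.

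**The case against.** The strongest reply is that shrinkage is assumed. No GM2 SD is readable, and the estimand in SAP 2.1.1 includes data regardless of adherence. Venglustat participants who have stopped drug, or who respond variably, widen that arm. The last table shows that modest amounts of either remove much of the shortfall, sometimes all of it, and R above 1 reverses it. This stands: 0.81 to 0.83 at a 50% reduction is the uniform-response case. It does not rescue the pooled model, whose interval is right only if the two spreads happen to match.

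A second reply is that the decision does not depend on this interval and that the SDs will be tabulated (SAP 3.2.1.2 and 3.7.2), so unequal spread would be seen. That is true, but tabulating SDs does not correct the reported interval.

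Three stronger readings are tempting, and the documents support none of them.

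- A reader might infer that the estimated effect is wrong. Unequal variance leaves the least-squares difference unbiased; only its SE and CI are affected.
- A reader might infer a risk of false success. If the drug does nothing, the spreads are equal and the test keeps its level.
- A reader might infer that placebo participants will be flagged as outliers, so that efficacy itself triggers the robust analysis. A common residual scale makes this possible, but the GM2 cut-off is not readable. The 9-HPT rule visible in the simulation code uses weighted residuals, and SAP 5.6.1 says the GM2 procedure differs somewhat. No switching rate can be given.

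**Conclusion.** The concern holds conditionally. As readable, the GM2 ANCOVA has no protection against unequal variances in a 2:1 design. If response is uniform and proportional, nominal 90% coverage falls to about 0.86 at a 30% reduction (0.84 to 0.86 across the runs), 0.81 to 0.83 at 50% and about 0.78 at 70%. With about 10% of the arm off drug or with variable response, it is about 0.86 to 0.90 at a 50% reduction. If venglustat widens the spread, the interval is too wide (0.93 to 0.94 at R = 1.25 to 1.5). All of this rests on assumed GM2 variability. The coverage figures are for percent change; for absolute change only the direction is argued. The consequence is limited to the reported SE and CI of one co-primary and one secondary endpoint. The improvement is cheap and worth making, but the trial's conclusion does not turn on it.

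**What to change.** In SAP 3.2.1.2 and 3.3.1.2.1, fit the ANCOVA with a separate residual variance per treatment arm (PROC MIXED, REPEATED / GROUP=treatment, Kenward-Roger df). This keeps the difference in means as estimand and gives about 90% coverage whichever arm varies more.

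In 5.6.1.1, check that the GM2 criterion standardizes residuals on an arm-specific scale, and say so.

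An analysis of log(Week 104 / baseline) may be added as a sensitivity analysis. It should not replace the main analysis, because back-transformation gives a geometric-mean change, whereas SAP 2.1.1 defines a difference in mean percent change.

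The cost is SAP wording and one model option before unblinding. The interval may be somewhat wider. In placebo-SD units the simulated half-width goes from 0.471 to 0.477 at R = 1, from 0.382 to 0.436 at 0.7, from 0.331 to 0.416 at 0.5 and from 0.292 to 0.402 at 0.3.

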4 STUDY DESIGN

4.1 OVERALL DESIGN

This is a multicenter, multinational, randomized, double-blind, placebo-controlled, 2-arm, 104-week study (primary population only) to assess the efficacy and safety of venglustat as compared with placebo in adult participants with a diagnosis of late-onset GM2 gangliosidosis (referred to as the primary population) and venglustat received in an open-label design in participants with a clinical diagnosis of juvenile/adolescent late-onset GM2 gangliosidosis, GM1 gangliosidosis, Saposin C deficiency, Sialidosis Type 1, or juvenile/adult galactosialidosis if any of the sites have such participants meeting the inclusion and none of the exclusion criteria (referred to as secondary population). The secondary population is composed of participants with juvenile/adolescent late-onset GM2 gangliosidosis and ultra-rare conditions within the same biochemical pathway as the primary population. The 104-week treatment period (primary analysis period) will be followed by an OLE period with venglustat treatment for all patients. The study will be conducted at multiple, multinational sites (approximately 30 sites).

The study will include 4 main periods:

1. Period 1 (screening period from Day -60 to Day -1): Participant and/or participant's parent(s)/legal guardian(s) will sign and date the informed consent and the participant will undergo screening assessments to determine participant eligibility. If all eligibility criteria are met, the participant will start study treatment.
2. Period 2 (primary analysis period, 104-week treatment period): Participants in the primary population will be randomly assigned in a 2:1 ratio to receive venglustat or placebo once daily for 104 weeks in a double-blind manner. Randomization will be stratified on the participant's ability to walk at the baseline visit (yes/no). Participants in the secondary population will receive venglustat for 104 weeks in an open-label manner. Safety, tolerability, PK, PD, and efficacy of venglustat once-daily administration will be determined during the 104-week treatment period.

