3.3.1.2.3 Change in FARS-neuro

The FARS neurological score will be derived from the 23 items of the FARS-neuro (see [Section 5.5.3](#) for the derivation of the score).

Change in FARS-neuro will be compared between venglustat and placebo using a linear mixed-effect model with random intercept and slopes, similar to the analysis of the 9-HPT (see [Section 3.2.2.2](#)). The model will assume linear change over time in the FARS-neuro. No logarithm transformation will be performed for FARS neurological score.

Slope on venglustat and on placebo will be estimated from the linear mixed effect model. Efficacy of venglustat will be based on the comparison of slopes. The difference in slopes will be estimated and presented with its associated 90% confidence interval and p-value. Significance level will be the same as for the primary endpoint.

In case of outliers, the linear mixed-effect model will be replaced by the robust ANCOVA on individual slopes, described in [Section 3.2.2.3.1](#). The exact criterion to determine whether the robust ANCOVA should be used is presented in [Section 5.6.1.2](#).

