5.6.1.2 Criteria for 9-HPT, 25FWT and FARS-neuro

Potential outliers will be identified from the weighted standardized residuals, estimated from a robust ANCOVA on individual slopes, with treatment effect (venglustat versus placebo) as factor and the continuous fixed covariate of baseline value.

The robust ANCOVA will be used as primary analysis for the slope analysis

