```
/* Calculate weights and standardize them (so that mean weight = 1 and sum of
weights = n) */
proc means data=SimData nopolish nway;
  where nobs >= 2;
  class diff sce pE mE sE sim subject group base;
  var time;
  output out=css(keep=diff sce pE mE sE sim subject group base css) css=css;
run;
proc means data=css nopolish nway;
  class diff sce pE mE sE sim;
  var css;
  output out=meancss(keep=diff sce pE mE sE sim meancss) mean=meancss;
run;
data weight;
  merge css meancss;
  by diff sce pE mE sE sim;
  W = css/meancss;
run;

/* Include weights in the simulation dataset */
data indSlope;
  merge indSlope(keep=diff sce pE mE sE sim subject group base slope)
  weight(keep=diff sce pE mE sE sim subject group base w);
  by diff sce pE mE sE sim subject group base;
run;

/* Create observations from both groups, with baseline = mean baseline */
/* In order to obtain predicted mean slope from the PROC ROBUSTREG */
/* (this is because PROC ROBUSTREG has no LSMEANS or ESTIMATE statement) */
proc means data=simdata nopolish nway;
  where time = 0;
  class diff sce pE mE sE sim;
  var base;
  output out=meanbase(keep=diff sce pE mE sE sim base) mean=base;
run;
data pred;
  set meanbase;
  subject = 99.1; group = 0; W=1; output;
  subject = 99.2; group = 1; W=1; output;
run;

/* Include additional observations in the dataset for PROC ROBUSTREG */
data dataRobust;
  set indSlope pred;
run;
proc sort data=dataRobust;
  by diff sce pE mE sE sim subject;
run;

*****/*
/* STEP 3 : Analysis of simulated data with linear mixed-effect model */
*****/

ods listing close;
```

```
options nonotes;

/* Linear mixed-effect model */
proc mixed data=SimData;
  by diff sce pE mE sE sim;
  class subject group;
  model log9hpt = group time group*time;
  random int time / sub=subject type=un;
  estimate "Diff" int 0 group 0 0 time 0 group*time -1 1 / cl;
  ods output estimates=LMMeStimates;
run;

ods listing;
options notes;

/* Get estimate of difference of slopes and calculate 1-sided p-value */
data LMM;
  set LMMeStimates;
  LMMPvalue1S = probt(estimate/stderr,DF);
  keep diff sce pE mE sE sim estimate stderr lower upper LMMPvalue1S;
  rename estimate = LMMEst
        stderr    = LMMSE
        lower     = LMMLower
        upper     = LMMUpper;
run;

*****  
/* STEP 4 : Analysis of simulated data with robust ANCOVA */  
*****  
  
ods listing close;
options nonotes;

proc robustreg data=dataRobust order=data method=M(maxiter=100000);
  by diff sce pE mE sE sim;

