  class group;
  id subject;
  model slope = group base;
  weight w;
  ods output ParameterEstimates=RobustParameterEstimates;
  output out=RobustPred predicted=pred stdp=SE sr=stdres;
run;

ods listing;
options notes;

/* Get estimate of difference of slopes and calculate 1-sided p-value */
data Robust;
  set RobustParameterEstimates;
  where parameter = "group" and Level1 = "1";
  RobustPvalue1S = probnorm(estimate/stderr);
  keep diff sce pE mE sE sim estimate stderr lowerCL upperCL RobustPvalue1S;
  rename estimate = RobustEst
        stderr    = RobustSE
        lowerCL   = RobustLower
        upperCL   = RobustUpper;
run;
```

```
run;

/* Calculate number of patients with weighted standardized residual greater
than 3 and greater than 4 */
data outlier;
  set RobustPred;
  where subject notin (99.1,99.2);
  outlier3 = (abs(W*stdres) > 3);
  outlier4 = (abs(W*stdres) > 4);
run;
proc means data=outlier nopolish nway;
  class diff sce pE mE sE sim;
  var outlier3 outlier4;
  output out=Noutlier(keep=diff sce pE mE sE sim nOutlier3 nOutlier4)
sum=nOutlier3 nOutlier4;
run;

/*************************************************/
/* STEP 5 : Combine results and report simulation results */
/*************************************************/

/* Combine results from the linear mixed model and from robust ANCOVA */
data AllResults;
  merge LMM Robust Noutlier;
  by diff sce pE mE sE sim;

  * Hybrid approach: use robust ANCOVA if at least one patient with
  standardized residual > 4 or at least 2 patients with standardized residual >
  3;
  * otherwise, use linear mixed-effect model ;
  if nOutlier4 >= 1 or nOutlier3 >= 2 then do;
    Robust      = 1;
    HybridEst   = RobustEst;
    HybridSE    = RobustSE;
    HybridLower = RobustLower;
    HybridUpper = RobustUpper;
    HybridPvalue1S = RobustPvalue1S;
  end;
  else do;
    Robust      = 0;
    HybridEst   = LMMEst;
    HybridSE    = LMMSE;
    HybridLower = LMMLower;
    HybridUpper = LMMUpper;
    HybridPvalue1S = LMMPvalue1S;
  end;

  * Determine if significant at 0.05 one-sided level ;
  LMMSign    = (LMMPvalue1S < 0.05);
  RobustSign  = (RobustPvalue1S < 0.05);
  HybridSign  = (HybridPvalue1S < 0.05);

  * Coverage of 95% confidence interval ;
  LMMCover   = (LMMLower < diff < LMMUpper);
  RobustCover = (RobustLower < diff < RobustUpper);
  HybridCover = (HybridLower < diff < HybridUpper);
```

```
* Bias in difference ;
LMMBias = LMMEst - diff;
RobustBias = RobustEst - diff;

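### Randomization is stratified by ability to walk, but the main models for CSF GM2, 9-HPT and FARS-neuro and their robust fallbacks leave the factor out: a small, conditional loss of efficiency with no threat to validity

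*SAP*

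**What the plan says.** Protocol 4.1 and SAP 1.1 stratify the 2:1 randomization by whether the participant can walk at baseline. The analysis models are:

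- **CSF GM2, percent change (SAP 3.2.1.2):** an ANCOVA "including the fixed effect of treatment (venglustat versus placebo) and the continuous fixed covariate of baseline value". Its robust version has the same terms. Absolute change (SAP 3.3.1.2.1) "will be analyzed with the same approach used for percent change".
- **9-HPT (SAP 3.2.2.2):** "The model will include separate slopes for the venglustat and placebo arm", with random intercept and slope. The code in SAP 5.6.3.3 reads "model log9hpt = group time group*time".
- **Robust ANCOVA on individual slopes (Protocol Table 6):** treatment and baseline value only. The code reads "model slope = group base".
- **Outlier-detection fit for the slope endpoints (SAP 5.6.1.2):** "with treatment effect (venglustat versus placebo) as factor and the continuous fixed covariate of baseline value". The CSF GM2 fit in SAP 5.6.1.1 has the same terms.
- **FARS-neuro (SAP 3.3.1.2.3):** a mixed model "similar to the analysis of the 9-HPT".

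The MMRM sensitivity analysis (SAP 3.2.2.3.3) also has no walking term. Ability to walk enters a model only in the subgroup analyses (SAP 3.2.3 and 3.3.1.5). The 25FWT analysis is restricted to participants who can walk, so the factor does not apply there. The visible text gives no reason for the omission elsewhere.

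**The concern.** Stratified allocation removes between-stratum differences from the true sampling error of the treatment comparison. A model without the stratum still counts those differences in its estimated error. If walking status predicts the outcome, the standard error is too large, the test runs below its nominal level and some power is forgone. The omission does not inflate type I error or bias the estimate.

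The stakes are modest but real. There are 57 participants and both co-primary endpoints must succeed. SAP 3.1 relaxes the level to 0.05 one-sided because the disease is rare, and a conservative test hands part of that allowance back.

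FARS-neuro gives a structural reason to expect a link with walking. Upright stability supplies 28 of its 117 points. If a non-walker scores the maximum on Tandem Walk (3) and Gait (5), which is an assumption, 8/117 = 6.8% of the scale cannot worsen in that stratum.

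**Working it through.** **Inputs (SAP 5.6.3.3 code):** 38 and 19 participants; slope SD 0.0192; residual SD 0.0791; intercept SD 0.4841; visits at 0, 0.25, 0.5, 1, 1.5 and 2 years; 10% exponential dropout by year 2; slope difference 0.0374; one-sided 0.05. **Assumptions:** 21% non-walkers (the wheelchair-bound share in the natural history data, Protocol 3.1) and exact 2:1 balance within each stratum (no block size is visible).

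**Reproducing the stated power of about 80%.**
- Mean visit time is 5.25/6 = 0.875, and the centered sum of squares is 2.969.
- Variance of one estimated slope = 0.0192² + 0.0791²/2.969 = 0.000369 + 0.002107 = 0.002476 (SD 0.0498).
- Analytic power is 84.9% without dropout and 81.4% with the sample cut by 10%.
- Simulating the SAP's data-generating code gives 81.0% for a weighted two-stage slope analysis (6,000 trials), 78.8% for the REML random-slope model (480 trials, Monte Carlo SE 1.9 points) and 80.1% for the weighted Huber ANCOVA (2,000 trials).

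The stated figure holds.

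**Ceiling on the gain.** Only an effect of walking on slope matters in these models, because level differences go to the random intercept. Between-patient slope variance is 0.000369/0.002476 = 14.9% of the variance of a slope estimate, so walking status can explain at most that share.

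**Effect of the omission.** Let R² be the share of between-patient slope variance explained by walking, taken out of the SAP variance rather than added to it. The implied slope gap is √(R² × 0.000369/(0.21 × 0.79)). The standard error comes from the expected generalized-least-squares information for the slope, averaged over dropout patterns. The model's SE uses the full slope variance (0.01458). The true SE uses (1 − R²) of it.
- Type I error = P(Z > 1.645 × SE_model/SE_true).
- Power without the term = P(Z > (1.645 × SE_model − 0.0374)/SE_true).
- Power with the term = P(Z > 1.645 − 0.0374/SE_true).

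| R² | Slope gap per year | True SE | SE inflation | Type I error without term | Power without → with | Gain (points, before rounding) |
|---|---|---|---|---|---|---|
| 0% | 0 | 0.01458 | 0% | 5.0% | 82.1 → 82.1 | 0 |
| 25% | 0.024 | 0.01431 | 1.9% | 4.7% | 82.6 → 83.4 | 0.8 |
| 50% | 0.033 | 0.01403 | 3.9% | 4.4% | 83.0 → 84.6 | 1.6 |
| 100% | 0.047 | 0.01346 | 8.3% | 3.7% | 84.1 → 87.1 | 3.1 |

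**Simulation checks (12 non-walkers split 8:4).**

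| Analysis | R² 0% | 25% | 50% | 100% |
|---|---|---|---|---|
| Two-stage slope analysis, power without → with (6,000 trials) | 81.0 → 80.6 | – | 81.0 → 82.5 | 81.4 → 84.0 |
| Same, type I error without term | 5.0 | – | 4.1 | 3.4 |
| Weighted least-squares slope ANCOVA, power (20,000 trials) | 80.3 → 80.2 | 80.6 → 81.4 | – | 82.0 → 85.6 |
| Weighted Huber slope ANCOVA, power (2,000 trials) | 80.1 → 80.1 | – | 81.1 → 82.4 | 81.2 → 84.5 |

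**Outside the planning variance.** If walking adds a slope gap of 0.08 per year on top of the SAP slope SD (an assumption), the two-stage analysis gives type I error of 2.8% and power of 70.6% without the term, against 80.5% with it.

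**The case against.** The strongest reply is that no harm is shown. The tests are valid, and within the planning variance power never falls below the stated level. No visible passage says how strongly walking predicts 9-HPT slope or CSF GM2. If it explained 10% of between-patient slope variance, a further simulation puts power at 81.0% without the term and 81.4% with it. The 3.1-point figure needs one yes/no variable to explain all of that variance. This stands, and it keeps the point small.

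A second reply is that stratification was meant to balance walkers for the 25FWT analysis, as SAP 3.3.1.2.2 says. That explains why the trial stratified. It does not explain why the other models drop the factor. The subgroup models do include walking status, but they do not decide the co-primary tests.

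A third reply is that the change also alters the outlier trigger, so the operating characteristics of the switch to robust ANCOVA would be unverified, with perhaps 4 placebo non-walkers in a Huber fit. A close approximation of that hybrid was therefore simulated: a weighted slope regression in place of the mixed model, plus the Huber fallback and the trigger. With the term, type I error is 5.2–5.5% and the trigger rate moves by at most about 1.4 points. Power is 82.6% with or without the term if walking is not prognostic, and 84.0% against 82.3% at R² of 50%. The sponsor should still rerun its own code.

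SAP 3.2.2.3.1 and parts of SAP 5.6 are not visible, so a reason could be stated there. The fallback model itself is clear from Protocol Table 6, SAP 5.6.1.2 and the code.

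**Conclusion.** The concern holds as a low-priority efficiency point. Analyses of a stratified trial leave out the stratification factor, which makes them mildly conservative if that factor is prognostic. For 9-HPT the forgone power is roughly 1 to 4 points across the calculations when walking explains 25–100% of between-patient slope variance, and nil when it explains none. It could exceed this only if walking adds slope variance beyond the planning value. For CSF GM2 the gain is under 1 point because stated power already exceeds 99%. For FARS-neuro it cannot be computed, since no SD is given. The size rests on the SAP's variance inputs, the 21% non-walker share and balance within strata. The prognostic strength of walking status is unknown.

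**What to change.** Before unblinding:

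1. Add ability to walk, as randomized, to the CSF GM2 ANCOVA and its robust version, for both percent and absolute change.
2. Add stratum and stratum-by-time to the 9-HPT and FARS-neuro mixed models. A main effect alone would gain little.
3. Add stratum to the robust ANCOVA on individual slopes and to all outlier-detection fits, so that the fallback and its trigger match the main model.
4. Rerun the existing simulation code with these terms.

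Alternatively, state in the SAP why the factor is left out. 25FWT needs no change.

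The cost is SAP wording, one model term (two in the mixed models) and the rerun, with no new data. If walking is not prognostic, the loss is 1–2 degrees of freedom: 0 to 0.4 points of power in the simulations (for example 80.3% to 80.2%, or 81.0% to 80.6%).
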